Objectives: To evaluate the impact of LSQ on (1) participation in physical therapy using Pittsburg Rehabilitation Participation Scale; (2) quality of life using Quality of Life – Alzheimer’s Disease Scale (participant’s version); and (3) depression symptoms using Cornell Scale for Depression in Dementia (CSDD).

Methods: A consecutive sample of convenience of up to 60 patients with mild to moderate cognitive impairment with 44 (22 per group) completing the study will be recruited from a nursing home facility. Patients will be randomly allocated in two groups: (1) *Control group*, which will receive standard physical therapy care without LSQ use; and (2) *Experimental group*, where physical therapists will use the LSQ. Each patient’s family member will receive a LSQ to complete prior to the start of the intervention. Patients’ participation, quality of life and depression symptoms will be measured on day 1 and again after 3 weeks (mid-term), and 6 weeks of intervention. Quality of life and depression symptoms will also be measured 6 weeks following intervention. A licensed occupational therapist blinded to the participants’ group allocation will measure all three dependent variables

Statistical Analysis: Descriptive statistics including means, standard deviations, frequency counts, median, mode, variance and frequency counts will be used to assess sample demographics. The Rank Sum test will be used to assess differences in Pittsburg Rehabilitation Participation Scale between the intervention and control group. Spearman Rank correlations will be used to determine the strength of the correlation between Mini-Mental state examination, Pittsburg Rehabilitation Participation Scale and Quality of Life Alzheimer Disease.

Key words: Dementia, Life story questionnaire, Physical therapy, Participation, exercise

Financial Disclosure and Conflict of Interest: The investigators affirm that they have no financial affiliation (including research funding) or involvement with any

commercial organization that has a direct financial interest in any matter included in this manuscript.

NON-SCIENTIFIC ABSTRACT

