Background: Dementia is a general term for difficulties remembering, thinking or making decisions. Dementia increases among people aged 65 years or older. Exercise benefits dementia patients, however participation in activities is very difficult due to difficulties communicating and understanding. Several studies demonstrated that life story books usage improved quality of life, depression symptoms, moods and participation in activity in people with dementia. However, these studies did not evaluate the effect of Life Story Questionnaire (LSQ)– a type of life story book - on physical therapy participation, depression symptoms, and quality of life.

Objectives: To see the benefits of LSQ on (1) participation in physical therapy; (2) depression symptoms; and (3) quality of life.

Methods: Up to 60 patients with mild to moderate cognitive impairment with 44 (22 per group) completing the study will be recruited from a nursing home facility. Patients will be allocated in two groups: (1) *Control group*, which will receive standard physical therapy care without LSQ use; and (2) *Experimental group*, where physical therapists will use the LSQ. Each patient's family member will receive a LSQ to complete prior to the start of the intervention. Patients' participation, quality of life and depression symptoms will be measured on day 1 and again after 3 weeks (mid-term), and 6 weeks of intervention. Quality of life and depression symptoms will also be measured 6 weeks following intervention. An occupational therapist will take the measurements.

Statistical Analysis: Appropriate statistics will be used to analyze the data.

LIST OF ABBREVIATIONS

Cornell Scale for Depression in Dementia.....	CSDD
Life story books.....	LSBs
Life Story Questionnaire.....	LSQ
Mini-Mental State Examination.....	MMSE
Quality Of Life – Alzheimer’s Disease Scale.....	QOL-AD

BACKGROUND

Dementia is a devastating disease that places a significant physical, emotional and financial burden on patients, their caregivers and society¹. In 2015, the number of people living with dementia worldwide was estimated at 46.8 million. This number is expected to increase to 74.7 million in 2030 and 131.5 million in 2050². In the US alone, dementia was responsible for a total expense of US\$277 billion in 2018, and is expected to reach approximately US\$1.1 trillion in 2050³.

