Aims: The study plans to evaluate the impact of LSQ use on participation in physical therapy, quality of life and depression symptoms in people with cognitive impairment. The intervention will include gathering LSQ information for selected subjects from family patient/family members and then using this information for 6 weeks to evaluate the impact of LSQ on (1) participation in physical therapy using the Pittsburg Rehabilitation Participation Scale (Appendix B); (2) quality of life using the Quality of Life – Alzheimer’s Disease Scale (participant’s version) (Appendix C); and (3) depression symptoms using the Cornell Scale for Depression in Dementia (CSDD) (Appendix D).

Value: Previous studies demonstrated psychosocial life story book usage benefitted people with dementia in nursing homes, their relatives, and staff¹²⁻¹⁴. As per Woods et al. the life story book is beneficial to improve cognitive function, communication, quality of life and mood. However, randomized comparison trials are needed to evaluate the effect of life story book usage on physical therapy participation. People with dementia demonstrate challenges in physical therapy participation due to poor cognition and communication. Physical therapists are challenged to develop plans of care for people with dementia due to poor cognition. The LSQ can help develop individualized and person-centered care. It is hypothesized that the LSQ will help increase physical therapy participation for

Dementia - Life Story Questionnaire – Physical Therapy

people with cognitive impairment and therefore improve their functional mobility, activities of daily living, depression symptoms and quality of life. If LSQ proposed benefits are substantiated, this study could be the first to highlight the importance of LSQ increasing physical therapy participation and improving depression symptoms and quality of life in patients with cognitive impairment.

RESEARCH QUESTIONS, HYPOTHESES AND VARIABLES

RESEARCH QUESTION(s) (RQs)-This project aims to answer the following research questions:

1. **RQ 1:** What is the effect of LSQ usage on physical therapy participation in people with cognitive impairment at 3 weeks(mid-term) and six weeks as compared to a control group?
2. **RQ 2:** What is the effect of LSQ usage on quality of life in people with cognitive impairment at 3 weeks(mid-term), six weeks and six weeks following intervention as compared to a control group?

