3. **RQ 3:** What is the effect of LSQ usage on depression in people with cognitive impairment at 3 weeks(mid-term), six weeks and six weeks following intervention as compared to a control group?
4. **RQ 4:** What is the relationship between cognitive impairment severity and physical therapy participation improvement at the end of the intervention (6 weeks)?

RESEARCH HYPOTHESES -This student has devised the following research experimental hypotheses

1. **Research Hypothesis 1:** LSQ usage will increase physical therapy participation in people with cognitive impairment at 3 weeks(mid-term) and six weeks as compared to a control group.

2. **Research Hypothesis 2:** LSQ usage will improve symptoms of depression in people with cognitive impairment at 3 weeks(mid-term), six weeks and six weeks following intervention as compared to a control group
3. **Research Hypothesis 3:** LSQ usage will improve quality of life in people with cognitive impairment at 3 weeks(mid-term), six weeks and six weeks following intervention as compared to a control group.
4. **Research Hypothesis 4:** Mild cognitive impairment will be positively associated with participation in physical therapy at six weeks following LSQ usage as compared to a control group.

COMPARISON VARIABLES

Independent Variable(s)-The student plans to use the following Independent Variable(s) (IV)

1. IV1: physical therapist use of LSQ
 - a. Level 1: LSQ usage
 - b. Level 2: no LSQ usage

Dependent Variable(s)-The Student plans to measure the following dependent variable(s) (DV)

1. DV1: Pittsburg Rehabilitation Participation Scale²⁵(Appendix B)
2. DV2: Quality of Life (quality of life - Alzheimer's disease scale - participant's version)²⁶(Appendix C)

3. DV3: Depression (Cornell Scale for Depression in Dementia (CSDD)²⁷(Appendix D)

Relationship Variable(s)- The investigator plans to use the following variables (RV) for RQ 4

1. RV1: Pittsburg Rehabilitation Participation Scale²⁵(Appendix B)
2. RV2: Mini-mental state of examination (MMSE)^{22,23} = Measure of dementia severity³ (Appendix E)

METHODS

Research Design

Prospective Randomized Control Trial. The trial will be registered on Clinicaltrials.gov.

Research Setting/Location

Peachtree Place (Dementia care facility), Weatherford, Texas. This study will be approved by Texas Tech University (TTU) Institutional Review Board (Lubbock Campus).

Power Analysis

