Family members of each patient will receive an LSQ to complete prior to the start of the intervention (Appendix A). Investigator 1 will conduct all physical therapy sessions for the study patients. Investigator 2, will collect the following dependent variables on day 1 of week 1, and on day 1 of third and sixth weeks:(1) Pittsburg Rehabilitation Participation Scale, which measures patients' participation in therapy; (2) Quality of Life - Alzheimer's disease scale; and (3) depression symptoms (Cornell Scale for Depression in Dementia). Additionally, Investigator 2 will record quality of life and depression at six-week following the intervention. Both investigators will enter their data using Texas Tech University Health Sciences Center password protected Qualtrics platform.

Both control and intervention groups will receive individual exercises that include strengthening, balance, gait, aerobic, endurance, dual cognitive motor tasks and exercises to improve activities of daily living and functional mobility²⁸. A pragmatic exercise program will be used for each participant needs based on physical therapy evaluation and goals. Each session will last approximately 60 minutes with five minutes warm up and five minutes cool down, three to five times per week for six weeks.

All patients will be charged for physical therapy services provided, as these services are standard of care, but there will be no charge for the LSQ use.

Upon completion of the trial, if LSQ results in outcomes improvements, the control group will receive six weeks of physical therapy using LSQ. All licensed therapists who participate in this research completed the Collaborative Institutional Training Initiative (CITI) training.

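### Study Sequence puts the on-treatment assessments on day 1 of weeks 3 and 6, about a week before the times given in both abstracts and RQ 4

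*Combined protocol and SAP*

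**What the plan says.** The only operational schedule is in Methods, Study Sequence. The blinded assessor "will collect the following dependent variables on day 1 of week 1, and on day 1 of third and sixth weeks". The variables are the PRPS, which Power Analysis names as the primary outcome, the QOL-AD and the CSDD. The same section sets a six-week programme of 3 to 5 sessions a week and adds a later visit for two of the three measures: "Additionally, Investigator 2 will record quality of life and depression at six-week following the intervention".

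Other sections time the on-treatment visits as follows:

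- Abstract, Methods: the outcomes "will be measured on day 1 and again after 3 weeks (mid-term), and 6 weeks of intervention".
- Non-scientific abstract, Methods: "again after 3 weeks (mid-term), and 6 weeks of intervention".
- RQ 1: the effect "in people with cognitive impairment at 3 weeks(mid-term) and six weeks as compared to a control group". RQ 2 and RQ 3 name the same on-treatment times.
- RQ 4: "physical therapy participation improvement at the end of the intervention (6 weeks").
- Hypothesis 4, the counterpart of RQ 4: "participation in physical therapy at six weeks following LSQ usage as compared to a control group".

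No section gives a visit window or says which description prevails.

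**The concern.** Day 1 of a week comes before that week's treatment, so a visit on day 1 of week 6 cannot also be a visit after 6 weeks of intervention. The abstracts and RQ 4 therefore describe measurements that Study Sequence does not schedule.

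At stake is what the primary outcome measures. The PRPS form (Appendix B) rates participation in a therapy session, so the visit date decides which session supplies the primary data. If the assessor follows Study Sequence and the report uses the terms of the abstracts, the 3-week and 6-week results will overstate the exposure behind them by about a week each. RQ 4 correlates the MMSE with participation at the end of the intervention, and it would be answered with a score from the start of the final week.

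**Working it through.** The documents give no study-day figures to reproduce, so the check is calendar arithmetic.

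**Inputs.** Visits on day 1 of weeks 1, 3 and 6, six weeks of treatment and 3 to 5 sessions a week (Study Sequence); visits after 3 and 6 weeks (both abstracts); end of intervention at 6 weeks (RQ 4); a CSDD rating period of the week before the interview (Appendix D).

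**Visit days.** Day 1 of week k is study day 7(k − 1) + 1. Week 3 gives 7 × 2 + 1 = 15, and week 6 gives 7 × 5 + 1 = 36. Three and six completed weeks end on days 7 × 3 = 21 and 7 × 6 = 42. If *after* means the next day, the dates are 22 and 43.

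| | Study Sequence | Abstracts and RQ 4 |
|---|---|---|
| Middle visit | day 15, 2 weeks completed | day 21 or 22, 3 weeks completed |
| Last on-treatment visit | day 36, 5 weeks completed | day 42 or 43, 6 weeks completed |
| Gaps between visits | 15 − 1 = 14 and 36 − 15 = 21 days | 20 or 21 days, then 21 days |

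**Shift.** 21 − 15 = 42 − 36 = 6 days, or 22 − 15 = 43 − 36 = 7 days.

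**Sessions completed before each visit.** Assume s sessions every week, 6s in all.

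- Before day 15: 2s/6s = 33% (6 of 18 to 10 of 30). The end of week 3 would give 3s/6s = 50%.
- Before day 36: 5s/6s = 83% (15 of 18 to 25 of 30).

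The documents do not say that the weekly count is constant. If it may vary between 3 and 5, the share before day 15 runs from 6/(6 + 4 × 5) = 6/26 = 23% to 10/(10 + 4 × 3) = 10/22 = 45%. The share before day 36 runs from 15/(15 + 5) = 75% to 25/(25 + 3) = 89%. In no pattern is half the course complete before day 15, and in every pattern the sessions of week 6 are not yet complete on day 36.

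**CSDD rating period.** The seven days before a day-36 interview are days 29 to 35, which is week 5. Before day 42 they are days 35 to 41 (6 of the 7 days of week 6), and before day 43 they are days 36 to 42 (all 7).

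**The case against.** The strongest reply is that no conflict was meant: *at 3 weeks* and *six weeks* are shorthand for visits in weeks 3 and 6, and *mid-term* simply names the middle visit. Part of this stands. The wording of RQ 1 to RQ 3 and the 3-week and 6-week rows of Appendix B can fit either schedule. The Aims, which speak of "using this information for 6 weeks to evaluate the impact of LSQ", give the length of LSQ use and not a visit date. None of these should be counted as contradicting Study Sequence. The reply fails for the two abstracts, which say after 3 and 6 weeks of intervention, and for RQ 4, which names the end of the intervention. The conflict lies between those three texts and Study Sequence.

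A reader might also infer more than the documents support:

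- *That the group comparison is biased.* Both arms follow the same schedule, so it is not.
- *That the trial loses power.* Power Analysis does not say when the pilot difference was measured, so the effect is unknown.
- *That the last on-treatment PRPS is missing.* It is early, not absent.
- *That the CSDD captures nothing of week 6.* The look-back week is week 5, but Appendix D lets many items be completed from direct observation of the patient, and the interview day itself is in week 6.
- *That Hypothesis 4 calls for a PRPS six weeks after treatment ends.* Its wording allows that reading, but RQ 4 places the same relationship at the end of the intervention.

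Appendix B also prints a PRPS row for the post-treatment visit, which Study Sequence does not list. That is a separate question.

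**Conclusion.** The inconsistency is real and should be fixed. Both abstracts and RQ 4 place the on-treatment assessments at the ends of weeks 3 and 6, while Study Sequence places them 6 to 7 days earlier, after 2 and 5 completed weeks. The day counts follow directly from the text. The 33% and 83% rest on a constant weekly session count, which is an assumption; the conclusion does not depend on it.

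The consequences are mislabelled time points, unequal visit spacing and no end-of-intervention PRPS for RQ 4. The randomised comparison remains valid. The documents do not show which schedule was intended, so the finding is that the texts must be made to agree.

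**What to change.** Reconcile the two abstracts, RQ 4 and Study Sequence to one schedule, in one of two ways:

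1. Amend Study Sequence so that the two on-treatment assessments fall at the last session of week 3 and of week 6, with a stated window. This matches the abstracts and RQ 4.
2. Keep the day-1 visits, and reword the abstracts, RQ 4 and the result labels to 2 and 5 completed weeks, dropping the term mid-term.

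Either way, state that Hypothesis 4 refers to the same time point as RQ 4.

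The second option changes wording only. The first moves two visits by about a week. The Research Project Timeline plans data collection from May 2023 to September 2024, so if collection has begun, participants already assessed must be reported at their actual times. Neither option needs an additional assessor or assessment.

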The Crisis Prevention Institute developed a Life Story Questionnaire (LSQ) (Appendix A), which is a type of life story book for people with dementia. The information about LSQ can be gathered from multiple sources, especially family members. It includes information about preferences and lifestyle. Preferences include coffee vs tea, nickname vs full name, early riser vs night owl, small groups vs large groups, brands of personal care products. Lifestyle examples include culture, faith, family, relationships, job history, home, childhood

home and neighborhood, accomplishments, daily routine, and emotional needs. Understanding patient's preferences, values, and motivation in life is the foundation of person-centered dementia care.

The LSQ allows caregivers to start conversations about topics that are important to each patient, can help establish rapport between caregiver and patient. Clinicians' LSQ knowledge for each patient gives dementia patients security because even when they do not remember life facts, clinicians can still provide relevance to patients, creating a sense of familiarity and personhood. Additionally, the LSQ helps reduce psycho-social behaviors such as anger, agitation and depression when caregivers thoroughly understand patients' likes, dislikes, preferences, interests, and background. The LSQ can be used as a person's identity keeper¹³.

Older people have low levels of physical activity and even lower for people with dementia⁷. Physical activity is a potentially modifiable risk factor to reduce the risk of developing dementia as it can provide beneficial effects on brain health and cognition⁷. Regular exercise can positively impact dementia related symptoms including depression, anxiety, attention-deficit/hyperactivity disorder¹⁶. Additionally, it can relieve stress, improve memory, help sleep quality, and boost overall mood¹⁶. In older dementia adults living in residential care facilities, physical exercise helped patients improve their balance and maintain their independence¹⁷. However, participation in physical therapy for people with dementia is exceedingly difficult due to cognitive impairments. Physical therapists may need to develop other strategies to ensure that people with dementia

receive the input they need, such as improving caregivers' involvement or incorporating exercises into more functional activities that can be undertaken with less supervision, while promoting self-efficacy¹⁸.

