each scale usage. After demonstration, Investigator 2 will record the three dependent variables measurements on the same patients twice, with at least 48hour interval between measurements. A minimum of five patients will be used. The intra-rater reliability of measurements on the two separate days will be calculated.

Study Sequence

Investigator 1 will conduct patients' screening (Appendix F) before they enroll the study to determine their eligibility. Participants with mild cognitive impairment (MMSE 19-23) demonstrating understanding of the research and the consent decision and indicating a willingness to take part will be asked to sign a consent form. For participants with moderate cognitive impairment (MMSE 10-18), both the potential participants and their legally authorized representatives will be asked to give consent to allow study participation.

Patients will be randomly assigned using block randomization with a 1:1 allocation ratio and randomly permuted block sizes of 2 to 6 based on severity of cognitive impairment. The randomization will be performed in R software (version 4.1.2, R Core Team) using the randomize R package (version 2.0). Each subject will be randomized to one of two interventions: (1) Control group, which will receive standard physical therapy care without LSQ use; and (2) Experimental group, where physical therapists will use the LSQ. The randomization file will be generated by Investigator 1 (Physical therapist) not involved in the data collection process, with the results stored in a spreadsheet accessible only to the investigator responsible for the subjects' group assignment. This investigator will

not participate in any data collection. Due to the nature of the study, participants will not be blinded to the group assignment and to the treatment they will receive. Investigator 2 measuring the dependent variables, however, will be blinded to the group assignment.

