Example of LSQ usage: [name] has been diagnosed with dementia and scores 15 (Mild Cognitive Impairment) on MMSE scale. His family has completed LSQ and submitted it to the facility. All Peach Tree Place employees have access to LSQ to facilitate patient care. Patient's LSQ mentioned that patient loves coffee, enjoys playing cards and likes everything about cars. This patient is always excited to come to therapy when physical and occupational therapists (clinicians) mention drinking coffee together. Once patient arrives in therapy room, the clinician plays different card games with this patient in standing, to improve standing tolerance, also use balance board to challenge standing balance and to facilitate functional mobility. The clinician talks about cars, shows variety of car magazines while working on leg exercises. So, this clinician used various information from LSQ for this patient to motivate and improve therapy participation.

Outcome Assessment:

1. Pittsburgh rehabilitation participation scale (Appendix B) – to measure participant's participation in physical therapy
2. Quality of life in Alzheimer's disease – participant's version (Appendix C) – to access quality of life in dementia participants

3. Cornell scale for depression in dementia (Appendix D) – to access depression symptoms in dementia participants

Data Analysis

Descriptive statistics (means, medians, modes, standard deviations, frequency counts, minimum and maximum values) will be calculated using Excel version 2017 and SPSS version 20 (IBM Corp. Released 2011. IBM SPSS Statistics for Windows, Version 20.0. Armonk, NY: IBM Corp.) for the subjects' characteristics including age, gender, marital status, education, severity of cognitive impairment (MMSE) and living with family prior to admission to the dementia facility and the dependent and relationship variables.

Inferential statistics: the following statistics will be calculated using Jamovi version 1.6.

Research Questions 1-3: Because the data are ordinal (Pittsburg Rehabilitation Participation Scale, Quality of Life Alzheimer Disease, CSDD), the Mann-Whitney U test will be used to assess differences between the intervention and control group.

Research Question 4: Because the data are ordinal (MMSE, Pittsburg Rehabilitation Participation Scale) Spearman Rank correlations will be used to determine the strength of the correlation between MMSE and Pittsburg Rehabilitation Participation Scale.

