APPENDIX A: Life Story Questionnaire

Professional Care Partners: Use this questionnaire to learn about the clients you work with. Complete one questionnaire with each client and/ or the client's loved ones. This great resource will provide you with helpful information as you get to know your clients and encourage their interests and abilities.

Family Care Partners: Use this questionnaire to help others learn about your loved one. Complete this questionnaire with your family member or on her behalf. With this valuable tool in hand, everyone who cares for your loved one will have the information they need to engage her likes and interests.

Background:

Full name _____

Does your name have a special significance?

Do you have a nickname?

Where did your nickname come from?

Where were you born?

What was your father's name?

Please describe your father.

What was your mother's name?

Please describe your mother.

Do you have brothers and/or sisters?

If yes, please describe your siblings.

Did you know your grandparents?

If yes, please describe your grandparents.

Where did you grow up?

Please describe the house you lived in.

What was your neighborhood like?

Who were your neighbors?

What games did you play?

Are/were you married?

If yes, please describe your spouse.

you have children and grandchildren?

If yes, please describe your children and grandchildren.

Daily Routine

What time do you like to get up in the morning?

Do you prefer to stay in your pajamas for a while?

Describe your routine after waking (e.g., brushing your teeth, doing your hair, dressing).

Do you prefer showers or baths?

At what time of day do you take a shower/bath?

Do you eat breakfast?

If yes, what do you like to eat for breakfast?

What's your typical lunch and afternoon routine?

Do you like to take naps?

Do you like a big meal at noon or in the evening?

Please describe your typical evening routine.

What time do you like to go to bed?

What hygiene products do you prefer?

Education Where did you go to school?

How did you get there?

What did you like about school?

Also ask questions about high school and college, if appropriate.

Work

What was your first paid job?

What kind of job was it?

What were your duties/responsibilities?

What were your accomplishments?

Leisure

What are your hobbies/interests?

What are your favorite movies/books?

Do you enjoy music? If yes, what kind?

Did you have pets? If so, what kind, and what were their names?

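### The control arm is not protected from the Life Story Questionnaire (LSQ): a form is sought for every patient, staff access is open and one therapist treats both arms, so the contrast is at risk of contamination

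*Combined protocol and SAP*

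**What the plan says.** - **Control condition (Methods, Study Sequence).** "Control group, which will receive standard physical therapy care without LSQ use". The factor under test, listed under Comparison Variables, is "IV1: physical therapist use of LSQ".
- **Who gets a form (Study Sequence).** "Family members of each patient will receive an LSQ to complete prior to the start of the intervention". Both abstracts also say that each patient's family receives one.
- **Who treats (Study Sequence).** "Investigator 1 will conduct all physical therapy sessions for the study patients". The same investigator generates the randomisation file. Only the outcome assessor, Investigator 2, is described as blinded.
- **Who can read the form (Study Sequence, Example of LSQ usage).** "All Peach Tree Place employees have access to LSQ to facilitate patient care". The example describes both physical and occupational therapists drawing on it. The form in Appendix A tells families: "With this valuable tool in hand, everyone who cares for your loved one will have the information they need".
- **Supposed mechanism (Background).** "the LSQ helps reduce psycho-social behaviors such as anger, agitation and depression when caregivers thoroughly understand" the patient's likes, dislikes and history.
- **Later LSQ therapy for controls (Study Sequence).** Controls are offered LSQ-based therapy only once the trial is over, and only if the LSQ has improved outcomes.
- **Analysis (Data Analysis).** Mann-Whitney tests between arms for Research Questions 1 to 3, by intention to treat.

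**The concern.** A no-LSQ arm needs some means of keeping the LSQ out of it. Here the forms are requested for control patients at the start of the study, the only stated access rule is open access, and the person who must refrain from using the content treats the control patients. The arm's label is its only protection.

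Two routes of exposure follow. For participation, the route is the shared therapist, who may come to know a control patient's history and preferences from the form. For the Cornell depression scale (CSDD) and the quality-of-life scale (QOL-AD), the route is other staff, because the Background itself credits caregivers' LSQ knowledge with reducing depression.

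At stake is the reading of Research Questions 1 to 3. If control patients received part of the intervention, a null result could not be told apart from contamination. Intention to treat rightly keeps such patients in the control arm, so the analysis cannot repair the problem. Without a record of LSQ use, its extent could not even be described.

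**Working it through.** **1. Do the passages combine as claimed?**

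- *Forms exist for controls:* the Study Sequence and both abstracts say each patient. The Aims paragraph speaks of selected subjects, which is ambiguous but does not exclude controls.
- *Forms can be read:* the access sentence makes no exception for control patients, and Appendix A agrees with it.
- *The therapist is shared:* all sessions in both arms are given by Investigator 1.
- *Safeguards:* the plan has no sealing, no delayed collection, no access limit, no log of LSQ use and no fidelity check.
- *Post-trial LSQ therapy for controls:* it comes after the last assessment, so it is not a source of exposure.

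**2. The plan's own sample size.** Inputs from Power Analysis: difference 0.5, SD 0.5, so d = 0.5/0.5 = 1; alpha 0.05; power 0.80; Mann-Whitney test; 22 per arm. Sidedness is not stated; two-sided is assumed.

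Method: noncentral t with the per-arm size multiplied by the asymptotic relative efficiency (ARE) of the Mann-Whitney test.

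- Normal-parent ARE, 3/π = 0.955: 18 per arm, 36 in total.
- Minimum ARE, 0.864: 20 per arm, 40 in total.

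The stated 44 is not reproduced from these inputs. The gap is on the conservative side and does not bear on this point.

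**3. Power under dilution (participation scale only).** Let c be the share of the LSQ effect that control patients also receive. The documents give no value for c, so a range is assumed.

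- Effective d = 1 − c
- Effective n per arm = 22 × 3/π = 21.01
- Degrees of freedom = 2 × 21.01 − 2 = 40.0
- Noncentrality = d × √(21.01/2) = 3.241 × d

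| Assumed c | Difference in scale points | Effective d | Noncentrality | Power, 22 per arm | Completers per arm for 80% power |
|---|---|---|---|---|---|
| 0% | 0.50 | 1.0 | 3.24 | 0.885 | 18 |
| 10% | 0.45 | 0.9 | 2.92 | 0.812 | 22 |
| 20% | 0.40 | 0.8 | 2.59 | 0.716 | 27 |
| 30% | 0.35 | 0.7 | 2.27 | 0.600 | 35 |
| 50% | 0.25 | 0.5 | 1.62 | 0.353 | 67 |

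With the minimum ARE the powers are 0.851, 0.770, 0.670, 0.556 and 0.323.

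Under the normal-parent ARE, 44 completers hold 80% power up to about 10% dilution. At 30%, 2 × 35 = 70 completers would be needed, more than the 60 the plan allows to be recruited.

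**4. What cannot be computed.** The plan gives no effect size for CSDD or QOL-AD, so no figure is offered for the other-staff route.

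**The case against.** The strongest reply is that the plan tests LSQ use by the physical therapist, not a facility free of the LSQ. Access by nurses or occupational therapists is then a background condition common to both arms, and it does not breach the control definition. This stands. It narrows the other-staff route to a possible shrinking of the added effect on CSDD and QOL-AD. It does not answer the shared-therapist route, and Research Questions 2 and 3 speak of LSQ usage in general rather than therapist use.

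It is also fair that the access sentence sits in an illustrative example about one patient, and that asking families for a form does not guarantee its return. But the sentence is worded as a fact about the whole facility, Appendix A agrees with it, and nothing limits it.

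The effect size of 1 comes from a pilot at the same facility. If access was similar then, some dilution may already be in it; the documents do not say.

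A reader might infer three stronger things that the documents do not support:

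- *That the contrast is diluted and all outcomes are biased towards no difference.* Only the risk is shown. A therapist who knows the allocation could also widen the participation difference through unequal effort.
- *That the follow-up comparison mixes continued exposure in one arm with uncontrolled exposure in the other, and so says nothing about persistence.* Research Question 2 asks "What is the effect of LSQ usage on quality of life in people with cognitive impairment at 3 weeks(mid-term), six weeks and six weeks following" the intervention, and Research Question 3 does the same for depression. LSQ information is to be used for six weeks, no text continues therapist use afterwards, and the access sentence makes no distinction between arms.
- *That both scales cover the whole preceding week.* Appendix D says so for CSDD. The QOL-AD items in Appendix C ask about the present or about lately.

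**Conclusion.** The point holds as a gap in the design. Followed as written, the plan creates LSQs for control patients, states open access to them, has one therapist treat both arms, and neither withholds the forms nor records their use. The between-arm contrast is unprotected, and contamination could not be detected afterwards.

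The size is unknown. The illustrative loss of power, from 0.885 to between 0.81 and 0.35, applies to the participation scale only. It rests on assumed dilution of 10% to 50%, a two-sided test, the plan's effect size of 1 and the normal-parent ARE. For participation the net direction of bias is uncertain. For CSDD and QOL-AD the risk is a smaller added effect of therapist use, which cannot be quantified from the documents.

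**What to change.** In the Study Sequence and its usage example:

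1. State that control-arm LSQs are either collected only after that patient's assessment six weeks post-intervention, or returned sealed and kept unopened and outside the facility record until then.
2. State that the all-employee access sentence does not apply to control-arm forms.
3. Have the therapist record LSQ use (yes or no) at every session in both arms.
4. If a resident already has an LSQ on file, or staff access cannot be limited, record this. Word Research Questions 2 and 3 to match the independent variable, as the effect that LSQ use by the physical therapist adds.

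The cost is a wording change, an envelope or later collection, and one extra item per session. Facility staff could not use newly collected control-arm forms for about 12 weeks (6 of treatment plus 6 of follow-up). This fits the existing plan to offer controls LSQ therapy only after the trial. Nothing here restricts staff use of experimental-arm forms or sets rules for care after week 6; the contrast can be protected without either.
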